### **6.2.7 Pharmacodynamic Endpoints Including Immunological Markers Analysis**

IFN Beta-1a ADA and NAb is measured at Day 1 Pre-dose and at Day 28 (or Early Termination or last day in ICU), MxA, CD73 and other biomarkers such as PIMs are measured on Day 1 Pre-dose and then daily until Day 14 in the ICU. These will be summarised categorically or

numerically (with the derived Last observation performed) according to Treatment group (FP-1201-Iyo/Placebo), Severity of ARDS (Moderate/Severe) and Overall using binary classifications (Positive/Negative) or the actual values and change from baseline for the FAS population depending on the type of variable. Separate supporting summaries by Country will be included.

For the categorical variable, the observed proportions with 95% Confidence Intervals (Clopper Pearson) at Day 28 (or Early Termination) will be analysed and displayed. The binary classification will involve the Cochran-Mantel-Haenszel hypothesis test with Severity of ARDS and Country as stratification variables.

For numeric variables the change from baseline at the Last observation performed will be used for the purpose of analysis. This will involve an Analysis Of Covariance (ANCOVA) model as for the Total SOFA scores in Section 6.5.5 and will include change from baseline value as the response variable.

As the PIMs biomarkers are considered exploratory, further sensitivity analyses may also be performed and the results will also be presented and justified in any supporting statistical reports.

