### 5.2 Administration

FP-1201-lyo 10 µg (or placebo) will be diluted in WFI near the patient/in the ICU. Once prepared, the dose must be administered to the patient immediately. The diluted FP-1201-lyo or placebo will be administered as an intravenous bolus injection via a central or peripheral line. The injection will be followed with a 5 mL flush of sterile saline (not provided).

FP-1201-lyo and placebo injections will be given once daily for 6 days. The injection should be given at the same time each day  $\pm 1$  hour providing the patient's condition allows this. If for any reason this is not possible, the treatment window may be extended by up to 4 hours. The reason for the delay must be entered in the e-CRF. Subsequent doses should not be delayed and should revert to the original time schedule (e.g., if the D1 dose was at 13:00, the D2 dose was delayed and given at 17:00, the D3 dose should be given at 13:00  $\pm 1$  hour).

No dose modifications or temporary cessations of study drug administration are allowed. If a delay beyond the 4-hour window described above is required, the patient must be withdrawn from study drug but all data must continue to be collected per protocol. Administration of a second course of study drug is not permitted.

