##### **6.5.2 Biomarkers: CD73 and Potential Inflammatory Markers (PIM)**

Blood samples for the CD73 and PIM assessments will be collected pre-dose on D1 (baseline) and daily from D2 to D14 as detailed in the Schedule of Procedures (Section 7.1, Table 5). Fourteen samples of 2.5 mL will be collected for CD73 and PIM; from these, samples will be prepared for the CD73 and PIM testing. CD73 and PIM blood sample preparation and sample storage details are provided in the Laboratory Manual. It is essential that the actual time and date of collection of each sample is recorded in the sample collection form provided with the laboratory kits. CD73 samples will be analysed centrally by Wieslab AB; PIM samples will be analysed at MediCity Research Laboratory, University of Turku, Turku, Finland.

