## 7 STUDY CONDUCT

For the purposes of this study, study day 1 (D1) is defined as the first calendar day (from midnight to the following midnight) of treatment with FP-1201-lyo or placebo. All days thereafter are defined as “Dn” (e.g., D2, D3, etc.) until D28. After D28 the study assessments are performed on D90 (3 months; either a clinic visit or telephone contact), D180 (6 months) and D360 (12 months).

Baseline assessments are defined as those assessments carried out in the screening period and before the first dose of study drug on D1. It is critical that the time from diagnosis of moderate or severe ARDS to administration of the first dose of FP-1201-lyo or placebo is less than 48 hours.

Unless withdrawn from study, all patients will receive study drug for 6 days.

All assessments in the period up to D28 are only to be performed when a patient is in the ICU. If an improving patient is discharged from the ICU during the short-term follow-up period then the assessments under ‘last day in the ICU’ will be carried out and the survival status and other endpoints must be assessed on D28.

There are three follow-up periods:

- Short term: D7 to D28
- Long term: D90 [3 months] and D180 [6 months]
- Extended: D360 [12 months] (last visit)

The end of the study will be the date of last patient/last visit at D360.

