### **7.2.4 Treatment Period: D2 to D6**

Assessments from D2 to D6 are only performed when a patient is in the ICU. The following assessments are to be done daily:

- Check patient survival
- Confirm patient is in the ICU
- Check whether the patient is on ventilation (refer to Section 6.1.1 for definition of UAB)
- Administer the study drug (FP-1201-lyo or placebo) as an intravenous bolus injection **24 hours ±1 hour after the previous day's administration.** If for any

reason this is not possible, the dosing window may be extended by **up to 4 hours**. The reason for the delay must be entered in the e-CRF (see Section 5.2) Subsequent doses should not be delayed and should revert to the original time schedule.

- Record SOFA scores
- Recording of vasoactive drugs and renal support
- Vital signs (temperature, BP and HR) must be measured and recorded in the morning between 04:00 and 10:00 using the values closest to 10:00 (if these values are representative of the patient's condition). All vital sign assessments must be taken at the same time point whenever possible.
- Haematology, biochemistry and urinalysis: samples must be taken daily in the morning between 04:00 and 10:00 using the values closest to 10:00
- MxA, CD73 and PIM samples for central testing are taken within 22 hours  $\pm 2$  hours after the previous day's administration of study drug, however before the next study drug dose.
- Recording of concomitant medications and therapies
- Recording of AEs

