#### ***7.2.5 Short-term Follow-up Period: D7 to D14***

On D8 to D14 all assessments should be performed at the same time of day as the D7 assessments were performed. The following study assessments and procedures will be performed:

- Check patient survival
- Confirm whether patient is still in hospital
- Confirm whether patient is in the ICU. Patients still requiring intensive care who are transferred to another hospital or healthcare ICU facility prior to D14 will be followed up to assess the days in ICU at D28
- Check whether the patient is on ventilation (refer to Section 6.1.1 for definition of UAB). Patients still on positive pressure ventilation who are transferred to another hospital or healthcare facility prior to D14 will be followed up to assess the VFD outcome at D28
- Record SOFA scores
- Recording of vasoactive drugs and renal support
- ECG is taken on D7
- Vital signs (temperature, BP and HR) must be measured and recorded in the morning between 04:00 and 10:00 using the values closest to 10:00 (if these values are representative of the patient's condition). All vital sign assessments must be taken at the same time point whenever possible
- Haematology, biochemistry and urinalysis: Samples must be taken daily in the morning between 04:00 and 10:00 using the values closest to 10:00
- MxA, CD73 and PIM samples for central testing taken at the same time as on D6  $\pm 2$  hours
- Recording of concomitant medications and therapies
- Recording of AEs

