## 8.10 Determination of Sample Size

For 90% power and a two-sided Mann–Whitney U-test at the significance level of 0.05, a total of 272 patients are required based on the following assumptions:

- mortality rate of 30% in the control group and 15% in the FP-1201-lyo group at D28
- 20% of patients survive but with zero ventilator-free days (VFDs) in the control group
- A mean difference (FP-1201-lyo minus control) of 3.0 days in mean ventilator-free days where patients who die are assigned a score of 0

However, assuming 5% of patients (16) drop-out and a further 4% (12) of the remaining patients will not be evaluable for the efficacy analysis, the study will randomise 300 patients to build in some flexibility around the assumptions listed above.

PASS software (Version 11; NCSS LLC, Kaysville, UT, USA) was used to calculate the required sample size for this study. Table 6 gives values for power based on this sample size and alternative values for the mortality rates in the two treatment groups with a total sample size of 300 (including 5% drop-outs and a further 4% non-evaluable patients). These calculations are based on the construction of two multinomial distributions according to the above assumptions and the associated non-parametric comparison of those distributions.

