### ***5.9.6 Strategy For Missing Data***

No biases resulting from missing data are anticipated and, as a consequence No imputation of any missing values at any of the assessments performed is planned.

However, to allow for patient attrition or any changes to the scheduled patient assessments as a consequence of the treatment response a 'Last observation performed' assessment will be derived for specific Short term efficacy (Ventilation assessment, System Organ Failure (SOFA), Cardiovascular, Pulmonary and Renal function), Pharmacodynamic (IFN $\beta$  ADA & Nab, MxA, CD73, PIM) and Safety variables (Vital signs and Laboratory assessments). This approach will use the last available non-missing post baseline value.

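### The one between-arm model specified for MxA and CD73 uses each patient's last sample up to D14, so it mixes values taken during dosing with values taken up to eight days after it

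*SAP*

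**What the plan says.** The analysis rule is in SAP 6.2.7: "For numeric variables the change from baseline at the Last observation performed will be used for the purpose of analysis". The model is the ANCOVA used for the total SOFA score. SAP 6.2.4.5 gives its terms: treatment, ARDS severity, country and the baseline value. SAP 5.6.2 (MxA) and 5.6.3 (CD73) place the last observation at D14 or earlier, and SAP 5.9.6 gives the general rule: "This approach will use the last available non-missing post baseline value". SAP 7.2.7 promises LS means and a 95% CI for the treatment difference from this ANCOVA and names no other time point for it. Optional sensitivity analyses are mentioned only for the inflammatory markers (PIMs).

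The sampling and dosing schedule is in the protocol:

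- Dosing (5.2): "FP-1201-lyo and placebo injections will be given once daily for 6 days".
- Number of samples (6.5.2): "Fourteen samples of 2.5 mL will be collected for CD73 and PIM". MxA follows the same days (6.1.2.5).
- Timing on D2–D6 (7.2.4): "MxA, CD73 and PIM samples for central testing are taken within 22 hours" of the previous day's dose, with a 2 h margin either way and before the next dose.
- Timing on D7–D14 (7.2.5): "MxA, CD73 and PIM samples for central testing taken at the same time as on D6", again within 2 h.
- Setting (Section 7): "All assessments in the period up to D28 are only to be performed when a patient is in the ICU".

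MxA from baseline to D14 is a secondary endpoint (Protocol 3.2.1). CD73 over the same window is exploratory (Protocol 3.2.4).

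**The concern.** The SAP describes both markers as induced by the drug, so the interval between the last dose and the sample matters when the arms are compared. The specified model lets that interval vary from patient to patient and does not adjust for it. What sets the interval is ICU exit, death, withdrawal, early stopping of study drug or a missed sample. All of these happen after randomisation, and ventilation and survival are what the trial expects the drug to change.

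Two things are at stake. If induction fades after D6, an estimate that pools samples from during and after dosing can understate the effect during dosing. If the drug alters ICU stay or survival, the arms can also differ in when their last samples fall, and the comparison is then affected by that difference. These markers would help a reader of a neutral primary result to tell absence of biological activity from activity without clinical benefit, so the modelled contrast should be interpretable.

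**Working it through.** **1. Number of samples.** One pre-dose sample on D1 plus one a day on D2–D14 gives 1 + 13 = 14, which agrees with Protocol 6.5.2. The ANCOVA uses 1 of up to 13 post-baseline values per patient.

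**2. Time since last dose.** Take doses at one clock time each day and samples 2 h before that time (22 h after the previous dose; from D7 the same clock time as D6). Then

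hours since last dose = 24 × (sample day − day of last dose) − 2.

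| Last sample | Last dose | Hours |
|---|---|---|
| D2 to D7, dosed the day before | previous day | 24 × 1 − 2 = 22 |
| D8 | D6 | 24 × 2 − 2 = 46 |
| D14 | D6 | 24 × 8 − 2 = 190 |
| D14, drug stopped after D1 | D1 | 24 × 13 − 2 = 310 |

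The last row can occur because Protocol 5.2 keeps collecting data after a patient is withdrawn from study drug. All figures are nominal, before the 2 h margins.

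**3. Is the model adjusted for this?** The terms in SAP 6.2.4.5 include neither sampling day nor time since dose, so a 22 h value and a 190 h value enter on the same footing.

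**4. How common could late last samples be? An illustration, not a bound.** The inputs are the Table 6 row that matches the assumptions in Protocol 8.10 ("mortality rate of 30% in the control group and 15% in the FP-1201-lyo group at D28"): zero-VFD survivors 14% active and 20% control, mean difference 3.0 days.

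- Remaining share per VFD value 1–28: (1 − 0.15 − 0.14)/28 = 0.71/28 = 0.02536 active; (1 − 0.30 − 0.20)/28 = 0.50/28 = 0.01786 control. Table 6 shows 2.5% and 1.8%.
- Check: the values 1 to 28 sum to 406. 0.02536 × 406 = 10.30 and 0.01786 × 406 = 7.25. The difference is 3.05 days, which reproduces the stated 3.0. The row therefore spreads VFD evenly over 1–28.
- Protocol 8.5.1.2 gives VFD 12 for unassisted breathing that starts on D16, so VFD = 28 − start day, and still being ventilated into D8 means VFD 0–20.
- Survivors ventilated into D8 or later: 0.14 + 20 × 0.02536 = 0.647 active; 0.20 + 20 × 0.01786 = 0.557 control.

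This assumes no re-ventilation, that ventilated patients stay in an ICU that takes study samples, and that no samples are missed.

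**5. Direction of any shift between arms.** Use the same row, with ICU exit on the day ventilation ends and last-sample days limited to D2–D14. The 28 VFD values then give last-sample days that sum to 290, and zero-VFD survivors reach D14.

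- Common part, active minus control: (0.71 − 0.50)/28 × 290 + (0.14 − 0.20) × 14 = 2.175 − 0.84 = 1.335 days.
- Deaths spread evenly over D2–D7 (mean 4.5): add (0.15 − 0.30) × 4.5 = −0.675, total +0.66 days.
- All deaths after D14: add (0.15 − 0.30) × 14 = −2.1, total −0.765 days.

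The sign depends on assumed death timing, which the documents do not give.

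**6. Size of the effect on the estimate.** The documents give no SD, decay rate or expected effect for either marker, so no dilution or bias figure follows.

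**The case against.** The strongest reply is that little hangs on this. MxA is in neither testing hierarchy (Protocol 8.5.2.1.1, SAP 6.1.3), CD73 is exploratory, and SAP 7.2.7 promises an estimate and interval for the numeric markers, not a test. That stands, and it limits the weight of the point.

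Second, the SAP does not break with the protocol. The endpoint window runs to D14, carrying the last observation forward is allowed where relevant (Protocol 8.2.1.4), and MxA methods are left to the SAP (Protocol 8.5.2.4). Post-dosing values belong to the endpoint, so replacing it with a D2–D7 average alone would narrow it. This also stands, and the remedy should keep the full window.

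Third, daily values and changes will be summarised by arm (SAP 6.1, 7.2.7), and figures are planned. The table and figure shells are not in the supplied text and might show daily differences with intervals. The by-assessment sentence in SAP 7.2.7 could be stretched to cover the ANCOVA tables, but SAP 6.2.7 is explicit about the time point. The summaries show the time course; the text specifies no adjusted contrast over the dosing days.

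Fourth, a reader might infer that Table 6 proves that most patients in each arm enter with a post-dosing value. It does not. Ventilated patients may be transferred out (Protocol 6.1.1 and 7.2.5, SAP 5.3.3.7), assessments may be missed (Protocol 7.2), and re-ventilation breaks the link between VFD and day (Protocol 8.5.1.2). The even VFD spread is a device of the power calculation, and it even includes VFD 28, which under this mapping would mean breathing unassisted before D1.

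**Conclusion.** The point holds as a weakness in the choice of analysis. The only between-arm model that the SAP text specifies for MxA and CD73 pools samples taken from about 22 h to 190 h after the last dose in patients dosed on schedule, and later still after an early drug stop. Post-randomisation events decide which sample counts. The estimate can therefore be affected by ICU stay, survival and treatment discontinuation as well as by the marker response.

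A reader might go further and conclude that the estimate is diluted or biased in a known direction. The documents do not support that: they give no decay rate, and the shift between arms changes sign with assumed death timing. The shares of about 65% active and 56% control with a last sample on D8 or later, counting ventilated survivors alone, hold only under the assumptions in step 4. No confirmatory conclusion is at risk. This is a worthwhile and inexpensive improvement that uses samples already scheduled.

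**What to change.** In SAP 6.2.7, for MxA and CD73:

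- Pre-specify a repeated-measures model on all daily samples D2–D14 with baseline, ARDS severity, country, treatment, day and treatment-by-day. Use an unstructured covariance with a stated fallback. Leave values after death missing and do not impute them.
- Report the treatment difference with 95% CI for each day to D14, which keeps the protocol's window, plus the D2–D7 average as the on-treatment contrast. A simpler route to that contrast is an ANCOVA of each patient's mean change over the available D2–D7 samples.
- Keep the last-observation ANCOVA as supportive.
- Correct the cross-reference to the SOFA model from Section 6.5.5, which does not exist, to 6.2.4.5.

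The cost is SAP wording and one more model, with no new samples. The limitation is that patients who die or leave the ICU before D7 contribute fewer and earlier days, and later daily estimates rest on those still in the ICU. Some dependence on post-randomisation events therefore remains and should be stated in the report.

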### ***6.3 Safety Evaluations***

Specific evaluations include: Vital signs, Twelve lead ECG, Physical examination, Adverse events and Laboratory safety tests (Biochemistry, Haematology, Urinalysis). Interval or Categorical data summaries (as appropriate) for the SS population will be used to assist clinical evaluation. No formal statistical analyses will be performed. All safety summaries will be presented according to Treatment group and Severity of ARDS (Moderate/Severe) but there will be no grouping by Country. Details are given in Section 7.3.

### ***6.4 Addendums Long Term and Extended Follow Up Efficacy And Safety Reports***

Data collected at Days 180 and 360 encompassing the Long Term and Extended Follow Up periods (Day 90 to Day 180, and Day 180 to Day 360, respectively) will be summarised separately and issued as addendums to the Clinical Study Report (CSR). Details are given in Section 7.4. Table shells are given in Appendix 5 and Appendix 6.

---

## **7. Presentation**

### ***7.1 General Information***

All data described in Section 5 and 6 will be presented in tables, figures and listings. Detailed 'shells' to accompany this section are located in Appendix 1 to 6.

All tables will be displayed as courier new font size 8pt, in a landscape orientated A4 Word document. Solid lines will be provided beneath all column headings and after the last row of data. Each summary table will be supported by individual subject data listings (Section 7.5).

All demographic and safety data summaries will be produced for the FAS and SS populations respectively according to Treatment group (FP-1201-lyo, Placebo).

Efficacy, Pharmacodynamic and Pharmacoeconomic data analyses and summaries will be produced for the FAS population according to Treatment group (FP-1201-lyo, Placebo), Severity of ARDS (Moderate/Severe) and Country (1-8). The denominator for all categorical data summaries will be the number of patients available in the population.

Graphical displays will be provided according to Treatment group (FP-1201-lyo, Placebo) Overall and by Severity of ARDS (Moderate/Severe).

A Consort diagram will be used to classify the number of patients enrolled: Assessed for eligibility, Excluded/Included, Randomised, Treated, Followed up after ICU confinement and Analysed (by population) overall patients and by Treatment group and according to Severity of ARDS (Table 14.1).

The following described tables, figures and listings will be included in the statistical report. Note: All listings will be output with the original Day 90 report, and the Day 180 and Day 360 addendums including all relevant additional data, e.g. adverse events and medications reported after Day 90, together with any other additional safety and efficacy data. Tables and figures will be output for the main report once 300 patients have completed short term follow up at Day 28, and long term follow up at Day 90. Additional tables and figures will be output after locking long term follow up data at Day 180, and subsequently after locking data reported at the extended long term follow up at Day 360. The Day 180 and Day 360 report addendums will be displayed according to Appendix 5 and Appendix 6 table shells.

## ***7.2 Output Formats***

### ***7.2.1 Overall Study Patient Group***

#### ***7.2.1.1 Disposition***

Overall study disposition details at Day 90 will be summarised by Treatment group (FP-1201-lyo/Placebo), Severity of ARDS (Moderate/Severe) and Country (1-8) and Overall for all patients considered for inclusion. This categorical summary will include details of the number of patients Screened, Randomized no medication, Randomized, Treated in the ICU (Day 1-28), Completed the Short Term Follow Up Day 7, Short Term Follow Up Day 14, Short Term Follow Up Last Day in ICU, Short Term Follow Up Day 28 and Long Term Follow Up (Day 90) and also the numbers actually assigned to each of the analysis sets. Additionally, all available data will be used to indicate the number and percentage of patients who have completed Day 180 and/or Day 360 at this time. Supporting listings will detail the reasons for screen failure (Tables 14.1.1). Tables 14.1.1 will be re-presented both on completion of the long term visit at Day 180 (including all available Day 360 data), and subsequently for the extended long term visit at Day 360 in the Addendum Day 180 and Day 360 reports.

The number of patients completing each of the study periods, with all reasons for discontinuation, will also be displayed.

The disposition will also include information on the proportion of patients who Completed treatment (Days 1-6 of dosing) and those who Discontinued treatment (Less than 6 and also less than 4 days dosing) in the Day 90 report (Table 14.1.2), together will all available discontinuation data for patients who have reached or would have reached Day 180 and/or Day 360. This table will be re-presented in the Day 180 Addendum report and include the number and percentage of subjects who completed Long Term Follow Up at Day 180 and those who discontinued before Day 180 with reasons for discontinuation together will all available patient completion/discontinuation data at Day 360. This summary will be repeated by country (Tables 14.1.2). Tables 14.1.2 will be represented once all Day 360 data has been locked.

Additionally, any potential Investigator unblinding details or death reports recorded at Days 180 or 360 will be listed separately in the respective Addendum reports.

Furthermore, study informed consent and genetic sampling informed consent and associated dates and times are listed by treatment group and subject.

